This primary outcome measures changes in number of migraine days per month before and during treatment. The number of migraine days per month will be captured using a validated headache questionnaire and scores as follows: 0-8 migraine days per month = low frequency episodic migraine, 9-14 migraine days per month = high frequency episodic migraine, 15-30 migraine days per month = chronic migraine.

[figure not shown]
Assessments of headache and sleep:

At screening (visit 1), headache severity and impact will be assessed based on patients' interviews and HIT-6. Sleep quality will be assessed using the Insomnia Severity Index.

(<https://cbtscience.files.wordpress.com/2014/02/insomniaseverityindex.pdf>).

On days 30, 60, 90 and 120, baseline and treatment impact on headache and sleep will be assessed using the Headache e-diary and the consensus sleep diary [Carney et al., (2012) *The consensus sleep diary: Standardizing prospective sleep self-monitoring*, Sleep Vol.35, No.2, pp.287-302], the latter of which captures total sleep time, sleep latency, wake after sleep onset, number of awakenings, quality, sleep efficiency, and trouble staying awake.

Study flow chart

B. Statistical Considerations

Sample Size Justification:

Although precise sample size calculations are difficult given the novelty of the hypotheses and hierarchical structure of the data, a simulation was created using the “SIMR” package in R and R-Studio. Enrolling $N = 100$ with 4 measurement occasions (baseline, M1, M2, M3) that are created by aggregating the daily measurements from each month provides sufficient power to detect even small associations between changes in sleep and migraine activity. For example, fitting a linear mixed effects model assuming a random intercept, a modest association between intercept and slope ($r = -0.50$), unit variances for the fixed and random effects (i.e., z-scores), and $\alpha = 0.05$, this sample size will provide 95% power (95%CI: 75.1% to 99.9%) to detect correlations between slopes (i.e., changes in migraine and sleep) as small as $r = 0.15$. Differences smaller than this magnitude are unlikely to be clinically meaningful.

Data Analysis:

To fulfill the study’s purpose, 4 hypothesis are being proposed:

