Hypothesis 1 – temporal relationship I: Fremanezumab partially prevents migraine by restoring some aspects of sleep disturbances. If this hypothesis is correct, fremanezumab-induced improvement in sleep disturbances will precede the improvement in headache (i.e., the reduction in migraine days per month).

Hypothesis 2 – temporal relationship II: Fremanezumab-induced improvement in sleep disturbances is secondary to the reduction in migraine days per month. If this hypothesis is correct, fremanezumab-induced reduction in migraine or headache days per month will precede the onset of improvement in sleep quality and quantity.

Hypothesis 3 – principle III: The prevention of migraine leads to improved sleep and reduced sleep disorders. If this hypothesis is correct, only fremanezumab responders will experience improved sleep or sleep disturbances whereas fremanezumab non-responders will not experience improvement of sleep disturbances. If this hypothesis is incorrect, sleep quality or quantity will not improve in fremanezumab responders.

Hypothesis 4 – principle IV: Fremanezumab-Improved sleep disturbances lead to reduced migraine or headache days per month. If this hypothesis is correct, only persons with improved sleep disturbances will experience reduction in number of migraine or headache days per month. If this hypothesis is incorrect, patients with improved sleep disturbances may be migraine treatment responders.

[figure not shown]
The primary analyses are designed to estimate the elements of the competing hypotheses (i.e., temporal changes in migraine and sleep). To contrast these hypotheses, we will employ multivariate multilevel regression models as summarized by MacCallum et al.⁷³ and Goldstein.⁷⁴ This approach to modeling within-person change does not have the limitations of a change score approach (i.e., unreliability of residualized change scores), or percentage change approaches (i.e., floor effects, heterogeneous variances) where predictors and outcomes are reduced to differences among measurement occasions. A multivariate modeling approach will allow a direct test of all study hypotheses while maintaining a conservative Type-I error rate. Briefly, parsimonious models will be specified for outcomes and lagged (Y_{t-1}) and synchronous (Y_t) representations of each of the proposed mechanisms modeling time with both linear and quadratic change parameters. This model form will

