capture the expected substantial early-treatment changes in mechanisms (emerging via reductions in daily headache probability and/or increased sleep quality), or more gradual changes that may occur over the full treatment period. The pre-treatment values and change parameters will be specified as individual-level random effects; this effectively allows a unique trajectory to be specified for each individual and for each outcome. These trajectories will then be aggregated using a series of fixed main effects and interactions that directly correspond to each of our specific hypotheses.

In hypothesis 1, lagged sleep trajectories (t-1, t-2, and t-3) are hypothesized to exhibit statistically significant associations with headache probability such that greater increases in sleep are associated with greater reductions in migraine activity. The opposite is assumed in hypothesis 2 where lagged headache trajectories are hypothesized to exhibit statistically significant associations with sleep such that greater reductions in migraine activity are associated with greater increases in sleep. The best fitting model, using lags of either/both will be estimated using nested models and likelihood ratio tests to evaluate the best fitting hypothesis.

Secondary analyses: In addition to testing primary hypotheses, this study will provide a rich source of data to examine effects on other mechanisms. First, analyses will consider questions of “for whom does treatment work?” We will test whether pre-treatment levels of outcomes lead to differential response to treatments (ie, association between intercepts and slopes), which could provide preliminary evidence that, for instance, individuals with worse sleep respond best to treatment. Second, we will estimate the primary models using additional dichotomizations such as ‘responders’ for both sleep and migraine activity (> 50% change). For these analyses, treatment phase (baseline, treatment) and responder (no, yes) will be fixed factors with associations between response groups evaluated using frequency counts and odds ratios (95%CI). In a final set of models, we will use three treatment phases (baseline, early treatment, late treatment) to examine the cross-lagged association of responders and non-responders by treatment phase.

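### The claim of a conservative type I error rests on the model being multivariate; no rule for lags or multiplicity supports it, and the planned likelihood ratio tests cannot rank Hypothesis 1 against Hypothesis 2

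*Combined protocol and SAP*

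**What the plan says.** All of this is in the combined protocol and SAP, mostly under B3.B, Data Analysis.

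- **Error control.** "A multivariate modeling approach will allow a direct test of all study hypotheses while maintaining a conservative Type-I error rate". No family-wise level, adjustment or testing order follows. An alpha of 0.05 appears only in the Sample Size Justification, without sidedness.
- **Lags in the model description.** "parsimonious models will be specified for outcomes and lagged (Y_{t-1}) and synchronous (Y_t) representations of each of the proposed mechanisms", that is, one lag and a synchronous term.
- **Lags in the test of Hypothesis 1.** "lagged sleep trajectories (t-1, t-2, and t-3) are hypothesized to exhibit statistically significant associations with headache probability", that is, three lags, with a predicted direction.
- **Lags in the test of Hypothesis 2.** "The opposite is assumed in hypothesis 2 where lagged headache trajectories are hypothesized to exhibit statistically significant associations with sleep". The number of lags is not given; three is implied by symmetry.
- **Choosing between the hypotheses.** "The best fitting model, using lags of either/both will be estimated using nested models and likelihood ratio tests to evaluate the best fitting hypothesis".
- **Outcomes.** Hypothesis 1 speaks of some aspects of sleep disturbance and of migraine days, but its model uses headache probability. Hypothesis 2 says that "fremanezumab-induced reduction in migraine or headache days per month will precede the onset of improvement in sleep quality and quantity". The sleep diary "captures total sleep time, sleep latency, wake after sleep onset, number of awakenings, quality, sleep efficiency, and trouble staying awake". Primary Outcome Measures (B3.A) names the Insomnia Severity Index and migraine days per month. The assessment paragraph, however, places the Index at screening and the sleep diary at days 30, 60, 90 and 120.

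**The concern.** The error rate depends on how many tests are made and on what counts as a positive result. A multivariate model settles neither. It produces correlated estimates from one likelihood, but each coefficient tested at 0.05 still carries its own 5% risk. The plan attributes conservatism to the model form and leaves open the things that would determine it: whether lags are tested singly or as a block, whether one significant lag is enough, whether the predicted sign is required, and which sleep variable is lagged.

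The second difficulty is the contrast the study is built around. The hypotheses are presented as competing, and temporal order is meant to separate them. A likelihood ratio test compares a model with a restricted version of itself. A model with only sleep-to-migraine lags and a model with only migraine-to-sleep lags are not restrictions of each other.

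At stake is a claim of temporal precedence made with more false-positive risk than readers are told, or a statement that one hypothesis fits best which no planned test supports.

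**Working it through.** **The plan's own figure.** There is no error rate to reproduce; the plan gives only the adjective. Its one computed statistical figure is power for a correlation between slopes, which does not bear on this point.

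**Inputs.** Alpha 0.05 (Sample Size Justification); three lags per direction (Hypothesis 1 as stated, Hypothesis 2 by symmetry) or one lag (model description); two directions. Two-sided testing is my assumption, because sidedness is not stated.

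**Rates with no true lagged effect.** For k independent tests where any one counts, the rate is 1 − (1 − α)^k.

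| Reading | Per hypothesis | H1 and H2 together |
|---|---|---|
| One joint 3-df test, or one single lag | 5% | 1 − 0.95² = 9.75% |
| Any of three lags, independent | 1 − 0.95³ = 14.3% | 1 − 0.95⁶ = 26.5% |
| Any of three, lag tests correlated 0.5 | 12.5% | 23.5% |
| Any of three, lag tests correlated 0.9 | 8.4% | 16.0% |
| Any of three, predicted sign only (0.025 each) | 1 − 0.975³ = 7.3% | 1 − 0.975⁶ = 14.1% |
| One single lag, predicted sign only | 2.5% | 1 − 0.975² = 4.9% |
| All three lags required | 0.05³ = 0.0125% if independent; about 2% at correlation 0.9 | at most twice that |

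The correlated rows come from simulated equicorrelated normal statistics, with the two directions independent.

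**Check by simulation.** Null autoregressive panels (100 persons, 40 times, 2,000 runs, autocorrelation 0 to 0.9) gave 12.6% to 14.0% per direction and 22.7% to 25.7% for the pair when any lag counted. With a joint 3-df likelihood ratio test they gave 4.3% to 4.9% and 8.6% to 9.9%. These panels had no random effects or time trends, so they check the multiplicity arithmetic and not the planned model.

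**Lag unit.** The power section aggregates the diaries to four occasions (baseline and months 1 to 3). If lags are months, a three-occasion lag exists for only 4 − 3 = 1 occasion per person. Headache probability suggests daily lags. The text does not decide.

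**Nesting.** There are four models: N (no cross-lags), S (sleep-to-migraine block only), M (migraine-to-sleep block only) and B (both).

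- N is nested in S and in M, and both are nested in B. Comparing M with B tests the sleep-to-migraine block (3 df). Comparing S with B tests the migraine-to-sleep block (3 df). Both tests are valid.
- S and M are not nested in each other. With three lags each they have the same number of parameters, so the difference is 3 − 3 = 0 df and there is no chi-square reference.
- If both blocks are significant, the procedure selects B and does not rank the directions. If neither is, it selects N. The plan assigns no conclusion to either case.

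**The case against.** The best defence is that likelihood ratio tests are the named tool and are naturally joint tests of a lag block. On that reading each hypothesis is tested at its nominal 5%. The direction is predicted, and listing all three lags may mean that all three are expected to be significant; either requirement lowers the rate. The words either/both imply a combined model, so each direction has a valid test, and a two-way relation is an outcome the plan admits.

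Much of this stands, and it rules out three stronger inferences.

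- **That the error is 14% and 26%.** Those figures need separate, independent, two-sided 0.05 tests with any one lag sufficient. The documents state no such rule. The figures are the top of a range.
- **That open outcomes raise it to about half.** Seven diary measures times two headache definitions gives 14 pairs, and 1 − 0.95¹⁴ = 51%. But the seven measures are what the diary captures, not a list of planned tests. Two primary outcomes are named, and Hypothesis 1 is worded in migraine days alone. What remains is an unnamed sleep variable, which is a specification gap.
- **That no valid test of the hypotheses exists.** Each direction can be tested against the combined model. Only the ranking lacks a test.

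The defence does not rescue the claim itself. A 5% test per hypothesis is nominal, not conservative, and two of them give 9.75%. Where a reading does hold the pair below 5%, the reason is a strict decision rule that the plan does not state, not the multivariate model.

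**Conclusion.** The point holds as a gap in specification and an unsupported claim. Under two-sided readings in which a joint test or any single lag counts, the error rate is about 5% to 14% per hypothesis and about 10% to 26% for Hypotheses 1 and 2 together. The upper ends assume independent tests and an any-lag rule. If only the predicted sign counts, the any-lag figures are about 7% and 14%. If all three lags are required, the rate is about 2% or less per hypothesis. The plan does not choose among these, so it cannot assert where it stands.

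The range leaves out Hypotheses 3 and 4, although the claim covers all four. One independent 0.05 test for each would give 1 − 0.95⁴ = 18.5%.

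The comparison problem is narrower but bears on the central question. The planned tests show whether each direction is needed. They do not show which fits better, and there is no rule for both or neither.

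**What to change.** 1. Fit one bivariate model with both lag blocks. Test each direction by a single joint likelihood ratio test that drops its block.
2. Hold family-wise error at 0.05 over the two tests, by Holm or at 0.025 each (1 − 0.975² = 4.9% if independent). If separate lag tests are kept, Bonferroni over six is 0.05/6 = 0.0083 each.
3. Name one sleep variable and migraine days as the confirmatory pair, and label all other sleep and headache measures exploratory.
4. Reconcile the one-lag and three-lag descriptions, and state whether a lag is a day or a month.
5. State in advance the conclusion when both, one or neither block is significant. Compare the directions by a method that does not need nesting, such as the difference in standardised cross-lag effects with a confidence interval, or AIC as description.
6. Delete *conservative*, and state the family-wise level and the hypotheses it covers.

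Holm and the particular comparison in step 5 are options; other pre-specified choices would serve.

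The cost is SAP wording and some power. The plan gives no power for a lag-block test, so as an assumption: a 3-df test with 95% power at 0.05 (critical value 7.81, noncentrality 17.17) keeps about 91% at 0.025 (critical value 9.35), and one with 80% (noncentrality 10.90) keeps about 71%. Holm loses less, because the larger p-value is tested at 0.05 once the smaller passes.

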Background about migraine and sleep: Most patients believe that many of their migraine attacks are triggered by sleeping too little, sleeping too much, have their sleep interrupted too many times during the night, poor sleep quality, not feeling well-rested in the morning hours after the sleep, etc. These common complaints gave rise to the notion that sleep disturbances are some of the most common triggers of migraine. Moreover, sleep disturbances may be a risk factor for chronification of migraine, the transformation of migraine from episodic to chronic form. If sleep disturbances can trigger migraine attacks or lead to its chronification, it is tempting to propose that drugs that prevent migraine may have an ability to restore normal sleep or attenuate certain aspects of sleep disturbances and by doing so, prevent the initiation of an attack by preventing or modifying its trigger.

Background on fremanezumab and the hypothalamus: Fremanezumab is an anti-CGRP monoclonal antibody and belongs to a class of drugs that effectively prevents migraine. In principle, the size of CGRP (about 150 kD) does not allow it to cross the blood brain barrier (BBB) and enter the brain. It is therefore believed to achieve its preventative effects by acting outside the brain. An exception to this thinking is the hypothalamus, a brain area where the BBB is relatively open and as a result, large molecules may gain some access to its neurons.

B3. DESCRIPTION OF RESEARCH PROTOCOL

A. Study Design – Overview, Methods, Procedures

Overview:

This is a within-person study design that examines treatment effects (changes) using high-resolution assessments. To complete the study, each participant will be observed using daily assessments of **migraine** and **sleep** outcomes before treatment (baseline: 0 to 30 days), and at 1, 2, and 3 months after treatment (injection 1: days 31-60, injection 2: days 61-90, injection 3: days 91-120). In essence, this creates an interrupted time-series design where repeated interventions are introduced at fixed intervals.

Methods:

The study involves 5 visits. The first and last visit will take place at the headache clinic, while the middle three will occur at the Clinical Research Center:

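### The plan names a same-row value of the other series alongside its lags; in any equation where that value follows the outcome, the lag test that separates Hypotheses 1 and 2 is biased

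*Combined protocol and SAP*

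**What the plan says.** All of this is in section B3.B, Data Analysis, unless stated.

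- Model class: "we will employ multivariate multilevel regression models", a joint model of sleep and headache.
- Terms: the models are specified for the outcomes and for lagged "and synchronous (Y_t) representations of each of the proposed mechanisms". No equation follows.
- Hypothesis 1: "lagged sleep trajectories (t-1, t-2, and t-3) are hypothesized to exhibit statistically significant associations with headache probability".
- Hypothesis 2: "lagged headache trajectories are hypothesized to exhibit statistically significant associations with sleep".
- Decision: "The best fitting model, using lags of either/both will be estimated using nested models and likelihood ratio tests".
- Time unit: the Overview of the design says "each participant will be observed using daily assessments", whereas the sample size paragraph works with four monthly aggregates. Data Analysis does not say which of the two t counts.

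The plan also does not say whether the night or the day comes first within a row, or whether each outcome's own lags are in its equation.

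**The concern.** Hypotheses 1 and 2 are rivals, and the lags are meant to separate them. A lag coefficient can do that only if the equation does not also adjust for something the outcome itself has caused.

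Suppose a row holds a night and then the day that follows. Headache on that day is partly a result of that night's sleep. If same-row headache is a covariate when yesterday's headache is tested as a predictor of tonight's sleep, the model holds fixed a quantity that depends both on the outcome and, through headache persistence, on the predictor. This induces an association between predictor and outcome that has nothing to do with the lag effect. If the row holds the day and then the night, the same thing happens to lagged sleep in the headache equation.

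The induced association grows with the effect in the competing direction. The likelihood ratio test ignores sign, so a spurious lag term in the wrong direction still improves fit and could be counted as support.

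**Working it through.** **Inputs.** From the documents: 100 participants, 120 diary days, lags 1 to 3, and unit variances (the z-score convention of the sample size paragraph). The plan states no figure for a lag effect, so there is none to reproduce; its power figure concerns correlations between slopes and does not enter here. The values of a, b, c and d below are assumptions.

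**Model, night-then-day rows.** S is sleep (higher is better) and H is headache:

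- S_t = a·S_{t−1} + c·H_{t−1} + e
- H_t = b·H_{t−1} + d·S_t + u

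The errors e and u are independent with variance 1. The coefficient Hypothesis 2 is about is c.

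**Effect of adding H_t to the sleep equation.** Given the previous row, S_t has mean m = a·S_{t−1} + c·H_{t−1} and variance 1, and H_t − b·H_{t−1} = d·S_t + u. Conditioning on H_t as well gives

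E(S_t | S_{t−1}, H_{t−1}, H_t) = [m + d·(H_t − b·H_{t−1})] / (1 + d²).

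The coefficient on H_{t−1} is therefore (c − d·b)/(1 + d²) instead of c. When c and d have the same sign, it reverses once |d·b| exceeds |c|.

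**Numbers.** The last column is a simulation of 100 × 120 days with a = 0.3, own lags kept, a person-specific quadratic trend removed, lags 1 to 3 and 200 replicates. The closed form does not include the detrending.

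| c | d | b | Closed form | Simulated |
|---|---|---|---|---|
| −0.20 | 0 | 0.5 | −0.20/1 = −0.200 | −0.200 |
| −0.20 | −0.1 | 0.1 | (−0.20 + 0.01)/1.01 = −0.188 | not run |
| −0.20 | −0.3 | 0.1 | (−0.20 + 0.03)/1.09 = −0.156 | −0.164 |
| −0.20 | −0.2 | 0.5 | (−0.20 + 0.10)/1.04 = −0.096 | −0.101 |
| −0.20 | −0.4 | 0.5 | (−0.20 + 0.20)/1.16 = 0.000 | −0.010 |
| −0.10 | −0.4 | 0.5 | (−0.10 + 0.20)/1.16 = +0.086 | +0.077 |
| 0 | −0.3 | 0.5 | (0 + 0.15)/1.09 = +0.138 | +0.130 |

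In the fifth row, significance in the right direction falls from 100% to 16%. In the sixth, the wrong sign is significant in 100% of replicates. In the seventh, a false effect appears in 100%, against 5% without the synchronous term. For c = −0.20, with b from 0 to 0.7 and d from −0.1 to −0.5, the closed form runs from −0.198 to +0.120.

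**Smaller effects.** With a = b = 0.3, c = 0 and d = −0.1 the closed form gives 0.03/1.01 = +0.030. On 100 × 120 rows (400 replicates, no random effects), significance in the wrong direction rose from 2.5% to 90%.

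**Binary daily headache.** In two simulated cases the coefficient moved from −0.198 to −0.070 and from −0.101 to +0.132.

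**Day-then-night rows.** Here the outcome is headache and the persistence that matters is that of sleep. The true effect of lagged sleep was set at log-odds 0.1 per SD, and the effect of headache on sleep at 0.05, 0.1, 0.2 and 0.3 SD. With the synchronous term in the model and sleep autocorrelation 0.3, detection was 98%, 85%, 34% and 5%. At autocorrelation 0.1 it stayed at 95–100%. With no true effect, wrong-direction significance was 12%, 31%, 87% and 100% at autocorrelation 0.3, and 4–23% at 0.1.

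**The other equation.** Where the same-row value precedes the outcome, it is a mediator. With a = 0.3 and d = −0.4, the coefficient of S_{t−1} in the headache equation is the total effect, 0.3 × (−0.4) = −0.120, without S_t. With S_t it is the direct effect, truly 0 (simulated −0.011). That is a change of meaning rather than this bias.

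**After removing the synchronous term.** With own lags kept, the simulated sleep-equation coefficients return to −0.200, −0.099 and 0.000 for true values −0.20, −0.10 and 0. With own lags also left out, a true −0.20 gives −0.297 (d = −0.4), and a true 0 gives −0.078 and is always significant (d = −0.3). Dropping the synchronous term is therefore not enough by itself.

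**The case against.** The strongest reply is that the plan never says the two terms share an equation. It names them together, but they could belong to alternative models, or the synchronous link could be a covariance in the joint model, which would not bias the lags in this way. Both hypothesis tests and the likelihood ratio comparison are stated in lags only. This stands, and it makes the point conditional. It does not remove it, because nothing in the plan keeps a same-row value out of the equation in which it follows the outcome.

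The second reply is that the day-and-night argument needs daily rows. This also stands. The wording about headache probability suggests days, and with four monthly occasions a third lag would leave one usable row per person (4 − 3 = 1), but the plan does not settle the unit. A reader might infer that exactly one of the two equations is affected. The documents do not support that: they give no within-row order, and with monthly aggregates effects may run both ways, so both equations could be affected.

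The third reply is that the size depends on the values chosen. That is correct: the range runs from nothing to full reversal. The exact cancellation to zero at d = −0.4, b = 0.5 is a single point where d·b equals c, and should not be read as typical.

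**Conclusion.** The concern holds conditionally. If the same-row value of the other series enters an equation in which it is affected by the outcome, the lag coefficient there becomes (c − d·b)/(1 + d²), given unit residual variances and own lags. Depending on d and b, a true effect is left almost intact, hidden or reversed, or a false one is created. All effect sizes are assumed. The study's premise is that sleep and migraine act on each other, so d = 0 is not a safe default.

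A reader might go further and conclude that the choice between Hypotheses 1 and 2 will be produced by this adjustment. The documents do not support that: they write no equation, state the tests in lags, and give no values that would fix the size.

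Still, this is more than missing detail. The plan names a term that, on its most natural reading, biases the primary comparison, and it leaves that choice open. It should be settled before the analysis.

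**What to change.** In the SAP:

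1. Write out both equations. Fit the lag tests on daily rows and state whether the night or the day comes first within a row.
2. In each equation, keep the outcome's own lags and only those values of the other series that precede the outcome in clock time. A same-row value that precedes the outcome counts as the first lag in that equation; one that follows the outcome is excluded.
3. If rows are monthly or the order cannot be fixed, leave the synchronous term out of both lag tests. Carry the same-row association as a covariance of the joint model, or report it separately as non-directional. A logistic headache model has no free row-level residual to correlate, so for binary headache use a latent-scale correlation or correlated random effects.
4. Require the lag coefficient to have the hypothesised sign as well as a significant likelihood ratio test. With three lags, say in advance whether this means the first lag or their sum.

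The cost is SAP wording: the diaries are already daily and a joint model is already planned. The downside is that same-row associations that cannot be ordered no longer count as evidence for either direction.
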